6.7 Potential Risks

Animal and human subjects studies to date have defined the parameters of the safety of the RENCA cancer macrobeads. In summary, the RENCA macrobeads have been well tolerated in murine tumor models, in cats and dogs with naturally occurring tumors of various types, where the RENCA macrobeads have now been implanted for periods of up to four years. Furthermore, in 13 humans with end-stage cancer implanted with the macrobeads (up to 17 months), no serious adverse events have been recorded which can be attributed to the macrobeads. Typically, the animals undergoing implantation have exhibited improved appetite, weight gain, and increased activity levels (the latter have been remarkable in at least one half of the animals treated). Adverse reactions observed to date have been 1) mild-to-moderate intraperitoneal chronic inflammatory reaction evident after 3 months in cats and dogs, but not mice; and 2) entrapment of some macrobeads in the feline and canine omentum. In the humans the reactions have been mild as well. Some subjects have experienced mild, intermittent fevers after implantation (generally resolved by four to six weeks after implant).

A mild-to-moderate inflammatory reaction to the intraperitoneal placement of the macrobeads has been noted in humans and veterinary patients, but not mice. In the cats and dogs, where the RENCA macrobeads have been implanted for periods of up to four years, this reaction becomes apparent beyond three months. It consists of a minimal to moderate increase in inflammatory markers, with no disruption of normal physiological functions, such as those of intestinal peristalsis or biliary or pancreatic drainage/secretion. Neither has it interfered with subsequent re-implantations of the RENCA macrobeads when indicated. In humans, implantation has led to an increase in inflammatory markers, with intermittent, self-limiting, low grade fevers in some cases. However, as observed in animals, the reactions were mild and not accompanied by clinical limitations.

Comparison of the reaction to the RENCA macrobeads with that seen with the porcine islet agarose-agarose macrobeads implanted in mice, cats and dogs described in IND BB-IND 9762 submitted April 9, 2001, is useful. In these experiments porcine islet-containing macrobeads were implanted in mice, Wistar-Furth rats, cats, and dogs with both streptozotocin-induced and naturally occurring insulin-dependent diabetes and in a large series of normal (non-diabetic) Sprague-Dawley rats. Beads have remained in some of the animals for long periods of time (in rats, 1 year; in cats for up to 6 years; and in dogs, over 3 years.) One subject in the Phase I clinical trial had the macrobeads in place for 24 months without any evidence of adverse effects. No significant toxicity, other than the chronic inflammatory reaction, has occurred as documented by clinical veterinary observations, laboratory blood chemistry results, or histopathological analysis of recipient organs and tissues after sacrifice by euthanasia.

Beyond macrobead removal (likely to be only partial (50-70%), but also not needed in any of the subjects treated with the macrobeads to date), whatever medical or surgical treatments are in the best interests of the subject and consistent with optimal medical care will be carried out with subject and/or family consent at any stage of the formal sixteen month protocol period and for the lifetime of the subject as the protocol indicates

A second potential adverse effect of the implantation of the RENCA macrobeads is the transmission of a murine virus to a human host. Theoretically, this could involve transmission of the virus to the subject without infection; clinically significant infection; and infection of a third party via exposure to the beads or to the potentially infected subject. Such risks are greatly reduced by the fact that the RENCA cell line has been maintained in our laboratory over many years and has been screened for known murine viruses, including those that present a possible risk of infection for humans. Although the RENCA cell line does require passing through Balb/c mice approximately three times a year to maintain its tumorigenicity, the mice used for this passing are from Charles River Laboratories, are pathogen-free to the most stringent possible standards, and are

maintained under strictly controlled animal care conditions. Furthermore, the passing process itself is carried out in the Rogosin laboratories under sterile conditions. The RENCA cells are routinely tested for microbiological contaminants during their maintenance in culture as well as after their incorporation into the agarose-agarose macrobeads so that the risk of their carrying any known infectious agent is eliminated. Clinical monitoring of the approximately 500 mice, cats and dogs treated to date, furthermore, has given no indication of any viral or other infection related to the implantation of the macrobeads.

The only virus identified to date in the RENCA cell line is the ecotropic (non-xenotropic) variant of the murine leukemia virus (MLV), an endogenous retrovirus that is not known to infect human cells. Literature reports (National Research Council, 1991) of its lack of ability to infect human cells have been confirmed in our laboratory using a standard co-culture protocol (for up to 30 days) with human 293, an embryonic kidney cell line. Thus, there is no evidence that this murine retrovirus variant poses any threat to humans. In the 30 subjects in the Phase I clinical trial there has been no evidence to date of the transmission of or infection with the MuLV.

Risks associated with the surgical procedure (including anesthesia) required for the implantation of the RENCA macrobeads will be those normally expected for such a procedure involving a simple abdominal incision. They will be dependent, of course, on individual subject risk factors, but no subjects with unacceptable risks for such a procedure will be admitted to this study. The performance of the abdominal incision and the placement of the macrobeads in the peritoneal cavity are both simple and minimally invasive.

Allergic reaction to mouse antigens is a potential risk. With respect to this risk the following procedures will be in place:

All subjects eligible for this protocol will be screened with available mouse allergen extracts using intradermal skin testing (Greer Diagnostics) initially to determine if a wheal and flare reaction is present, indicating the presence of human anti-mouse antibody. Positive and negative skin test controls will be done at the same time.

Data from repeated implantations of mouse RENCA macrobeads in dogs and cats with spontaneously occurring tumors of various types have not provided any clinical or laboratory evidence of sensitization to mouse proteins over periods of up to four years. It should also be noted that, over the period of 4 to 6 months after a given implant, the RENCA cells in the macrobeads die so that there is not an ongoing production of antigenic substances by the mouse cells after this time. The agarose itself has been well tolerated (except for local foreign body reaction) for periods of up to several years in studies with porcine islet macrobeads and for

up four years (the longest the veterinary patients have been followed to date) with the RENCA cancer macrobeads implanted up to five times. The beads have been tolerated without evidence of adverse reaction in humans now for up to 24 months. There has also been no evidence of recreation to mouse antigen skin testing in any of the subjects in the Phase I clinical trial.

Should a subject in the protocol develop evidence of sensitization to mouse proteins, appropriate local and systemic therapy (antihistamines, steroids) will be given. If the reaction is medically manageable, it should not be necessary to remove the RENCA macrobeads, given the gradual loss of cells within these beads. Should the reaction not be amenable to medical treatment removal of the beads will be performed via an open procedure, although complete retrieval may not be surgically possible (see below).

The total amount of blood drawn over the first 180 days of the study will be approximately 300 cc. This amount will hold constant for the subsequent study periods of the same length. The risk of mild anemia secondary to this blood withdrawal is low, but will be appropriately treated if present. The exact amount of blood to be drawn, as the study progresses past 6 months will depend on the subject's clinical status and the need for tests to monitor the patient's clinical status. As noted, the protocol blood drawing amounts will be constant in each of the 180-day study periods. In addition, the placement of an intravenous catheter involves the risk of bleeding around the needle site, local inflammation, pain or infection.

6.7.1 Procedures to minimize risks

In all cases, the Investigators will minimize risks by carefully screening subjects prior to admission to the study and by carefully monitoring their clinical status during the course of the study. The RENCA macrobeads themselves will be monitored carefully with rigorous GMP and GLP standards as defined in the IND application. The lack of adverse events attributable to the macrobeads evident in the Phase I trial is reassuring, especially with regard to the potential problems of peritonitis, viral transmission (eMuLV) problems interference with abdominal organ function, seeding of mouse tumor cells in the human peritoneal cavity and sensitivity to mouse antigens.

For phlebotomies and intravenous line placements, the usual sterile technique will be used and adequate pressure applied when the indwelling catheters are removed. Confidentiality will be observed for all data obtained from clinical or laboratory evaluations.

6.8 *Escape Arm (Withdrawal with/without Bead Removal)*

The RENCA macrobeads will be left in place in the peritoneal cavity for the life of the subject unless consideration of the removal of the macrobeads is occasioned by:

- Subject request;
- Principal Investigator, attending or consulting physician decision, and/or Safety Board/IRB/FDA decision that such removal is in the best medical interests of the subject.

The events or findings that would initiate such considerations/discussion include, but are not limited to:

- Any finding of Dose Limiting Toxicity (DLT) as defined above;
- Evidence of active e-MuLV viral infection in subject's cells/serum/plasma (i.e., transmission of MuLV from the mouse cells to the subject with active infection productive of a viral load in the subject);
- Chronic peritonitis reaction \geq grade 3. Although not specifically defined per se in the NCI Common Terminology Criteria for Adverse Events v3.0, several of the subcategories under the Gastrointestinal section are applicable. The GI-Other sub-category will be used: Peritonitis/Chronic Inflammatory Reaction.

Grade 1: Asymptomatic; radiographic (flat plate, CT, or MRI) or ultrasound imaging of peritoneal reaction.

Grade 2: Symptomatic: abdominal pain or tenderness or pain on palpation (direct, rebound); altered dietary habits (i.e., appetite, fluid intake); requirement of IV fluids <24 hours indicated; altered bowel function (mild constipation or diarrhea).

Grade 3: Symptomatic and severely altered GI function (e.g., inadequate oral caloric or fluid intake); IV fluids, tube feedings, or TPN indicated \geq 24hours.

Grade 4: Life-threatening consequences.

Any toxicity of Grade 2 or above as defined above in relation to the NCI CTCAE v3.0 or DLT, as defined immediately above, will initiate discussion of the possibility/ desirability/ necessity of the removal of the RENCA macrobeads. Any such discussion will necessarily involve multiple considerations including the

advisability of a surgical procedure in the subject and the best interests of that subject from a medical point of view. As such, all discussions will involve, at a minimum, the Principal Investigator, the subject's primary or attending physician, relevant consultants, and the Safety Board as appropriate, with notification of the IRB and the FDA. It should be noted and emphasized that it will not be possible to remove all of the macrobeads. 50 to 80% removal is likely to be possible, but the exact level of removal of macrobeads that is achievable will depend on many factors, most importantly the subject's overall health status and best medical interests. Again, the removal of any macrobeads has not been warranted in any of the humans implanted with them thus far.

6.9 Treatment of Adverse Effects

Should any subject in this Phase II trial of the RENCA experience an adverse event directly related to the Macrobeads or study-related procedures, all appropriate medical care will be provided at no cost to the subject.

7 DATA MANAGEMENT AND STATISTICAL ANALYSIS

The critical parameters of this Phase II trial are those related to efficacy. Various markers, such as C-reactive protein, amylase, liver function tests, cell counts, and cytokine levels, will be sampled and analyzed. Given the study design, we will undertake simple population comparisons designed for small samples (non-normal distribution) as well as simple trend analysis for selected parameters. The data from all subjects, including those who withdraw or are withdrawn from the study will be analyzed. All data will be analyzed using SAS software.

7.1 Determination of Sample Size

Seventy-four (74) male and female subjects with advanced pancreatic or metastatic, treatment-resistant colorectal cancer meeting the protocol inclusion criteria will be sought for this study. Each subject will serve as his/her own control with measurements obtained and evaluated in an unbiased manner. This means that changes from baseline to various post-treatment time points will be analyzed for some variables (such as tumor markers, for example). The confidence intervals for these changes will be calculated. Of course, it is not planned for the survival analysis which will use a retrospective patient population comparison as defined in the Statistical Analysis Plan (a copy of which is attached). The colorectal patient data from this study has already been used to plan a controlled Phase IIb protocol for colorectal cancer. Data from the pancreatic patients, when completed, will be utilized to plan a phase IIb controlled protocol for the pancreatic patients.

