The efficacy/safety population is defined as all evaluable subjects regardless of subject compliance with protocol procedures. This population will be used in the primary analysis for assessment of efficacy. Efficacy sub-analyses may be performed on various subsets of subjects, such as those with no major protocol deviations or those who continued in the study for the entire treatment period (i.e., did not withdraw prematurely). One of the sub-analyses will include efficacy response after one, two, three, and/or four implantations.

All evaluable subjects enrolled in the study who complete at least one implantation procedure will be included in the safety population and considered evaluable for toxicity and safety. The efficacy and safety populations do not differ. All treatment related toxicities will be recorded and then tabulated at the end of the study. All treatment related toxicities will be recorded and then tabulated at the end of the study.

Screen Failures

All subjects who sign an Informed Consent but for any reason are not implanted will be considered screen failures. These subjects will be listed and the reasons for not being implanted listed and described.

5. Descriptive analyses

Measured outcome variables will be summarized overall and by relevant demographic and baseline variables. Descriptive statistics such as frequencies and relative frequencies will be computed for all categorical variables. Numeric variables will be summarized using simple descriptive statistics such as the mean, standard deviation and range. A variety of graphical techniques will also be used to display data, for example, histograms, boxplots, scatterplots, etc.

6. Primary statistical analyses

The primary objectives are outlined in Section 3 of this protocol. The analysis will be performed as detailed in Statistical Analysis Plan (SAP).

7. Secondary statistical analyses

The secondary objectives are outlined in Section 3 of this protocol. The analysis will be performed as detailed in Statistical Analysis Plan (SAP).

8. Stopping rules

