3.2 Study Design

This is an open-label, non-randomized, single-center Phase II trial to evaluate the efficacy, safety and tolerability of RENCA cell-containing macrobeads implanted in Stage IV subjects with colorectal or pancreatic cancer in whom standard and accepted therapy such as chemotherapy, radiation and/or surgery have failed and who have chosen to not pursue other experimental therapies. Patients will be implanted with RENCA macrobeads, which will permanently remain in the peritoneal cavity even if patients discontinue from the study or begin a new therapy (e.g., chemotherapy).

Screening will occur within 28 days prior to implantation. Each eligible subject who signs an Informed Consent Form (ICF) will be considered as "enrolled". Subjects who sign an ICF but who are not implanted will be replaced. A total of 30 subjects (20 with colorectal cancer and 10 with pancreatic cancer) will be implanted. Detailed inclusion and exclusion criteria are given in [Protocol Section 4.3](#).

Subjects will receive up to 4 macrobead implantations, with at least 3 months between each implantation procedure. The primary focus of the trial is to estimate specific clinically important parameters for use in planning subsequent regulatory trials designed to more fully assess efficacy, safety and tolerability. Subjects will undergo formal safety and efficacy assessments for

120 days after their final implantation. After this formal phase of the trial has been completed, subjects will be followed for the duration of their lives.

Data output and analyses will be stratified by cancer type. There are no pre-specified comparisons between the two cancer types.

The study will end 120 days after the last active subject undergoes their last implantation.

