5 ANALYSIS POPULATIONS

All subjects who receive at least one implant will be included in all efficacy and safety evaluations and will be referred to as the Treated Population.

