10 EFFICACY ANALYSES

Efficacy parameters will be listed and summarized for all implanted subjects, stratified by cancer type. There will be no formal hypothesis testing and no group comparisons are currently planned. The primary efficacy outcome will be all-cause mortality, as defined above in [Section 3.3.1](#).

Secondary efficacy outcomes will be:

- Time from first implantation to death
- Time from diagnosis of Stage IV disease to death
- Changes from baseline based on MRI, CT or PET-CT scan, and other appropriate imaging techniques (e.g., sonography, bone scans, other x-rays) as indicated, if feasible.
 - In primary and/or secondary tumor size (volume, area) and
 - In state (necrosis, vascularization) on MRI, CT or PET-CT scan, and other appropriate imaging techniques (e.g., sonography, bone scans, other x-rays) as indicated.
- Change from baseline in tumor markers (CEA, CA19-9)
- Change from baseline in CA125 (as a marker of inflammation)
- Changes from baseline in:
 - Clinician Global Clinical Assessment
 - Activities of daily living
 - Symptom rating
 - Quality of life (QCQ-C30)
 - Pain scale
 - ECOG

- Additional exploratory efficacy outcomes may be analyzed if feasible and will be defined in the CSR

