10.1 Efficacy Outcomes

10.1.1 All-cause mortality

All-cause mortality for primary analysis is defined as time from date of the first scan showing disease progression after completion of prior treatment (time of origin, T_0) to death from any cause. Subjects still alive at the time of analysis will be censored at that time point.

Secondary analyses of time from first implantation to death, and time from diagnosis of Stage IV disease to death, will be analyzed similarly.

For all time-to-death analyses the Kaplan-Meier curves will be presented; respective 95% two-sided confidence intervals (CIs) will be calculated.

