10.2 Statistical Analysis Methods

- All statistical testing will be considered strictly exploratory as the study was not powered based on statistical considerations.
- Exact 95% CIs will be calculated for rates.
- Survival analysis methods will be used analyze time-to-event outcomes; for non-mortality outcomes, the term “survival” will still be used to describe non-occurrence of the event being analyzed. Kaplan-Meier plots with 95% CIs will be generated to show probability of survival as a function of time since implantation. In addition, Kaplan-Meier estimates of the median survival time will be reported.
- The relationship between times from diagnosis of Stage IV disease diagnosis to the primary analysis time of origin and primary analysis time of origin to death will be examined (if feasible) using Cox regression model and Kaplan-Meier curves.
- The relationship between time-to-event outcomes and tumor markers (and other covariates, if feasible) will be assessed using Cox regression. Kaplan-Meier plots will be produced for descriptive assessment.
- Survival comparisons by implantation number will be performed, if feasible.
- Other explorations of efficacy data may be performed (if feasible), such as:
 - Testing for effects of baseline values of tumor markers and presenting stratified descriptive statistics, if deemed appropriate.
 - Plotting chronological subject profiles of specific parameters; i.e., plotting a set of parameters over time on the same graph for a given subject.

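### Protocol 7.1 promises a retrospective survival comparison that the SAP neither defines nor plans, and the SAP's survival curve from T0 counts guaranteed time before implantation

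*Protocol*

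**What the plan says.** Protocol 7.1 sets survival apart from the outcomes for which each subject is his or her own control. It refers to a "survival analysis which will use a retrospective patient population comparison as defined in the Statistical Analysis Plan" and says that a copy of the SAP is attached. It adds that the colorectal data have already been used to plan a controlled Phase IIb trial. Protocol Appendix 3 (items 6 and 7) also leaves the primary and secondary analyses to the SAP and names no comparator.

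SAP section 10 states: "There will be no formal hypothesis testing and no group comparisons are currently planned". SAP 5 defines a single analysis population: "All subjects who receive at least one implant will be included in all efficacy and safety evaluations". SAP 10.1.1 gives the survival method: "For all time-to-death analyses the Kaplan-Meier curves will be presented; respective 95% two-sided confidence intervals (CIs) will be calculated". The only survival comparison listed is internal and optional (SAP 10.2): "Survival comparisons by implantation number will be performed, if feasible".

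All-cause mortality from T0 is the primary outcome for colorectal cancer in Protocol 3.1.1 and the primary outcome overall in SAP 3.3.1. The SAP's list of definitions makes T0 the first scan showing progression once prior treatment has ended, and requires that scan to come before the first implant. SAP sections 1 and 13 say the SAP overrides the protocol's statistical text and that differences will be explained in the study report.

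**The concern.** A single-arm survival curve cannot show efficacy without a reference. Protocol 7.1 appears to supply one, but the document it points to contains none. A reader of the protocol would expect an external comparison, and a reader of the SAP would expect a descriptive curve. If a comparison were added later, nothing in the documents would fix its source, eligibility, time origin or adjustment, and the colorectal data have already been examined for planning.

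The second problem does not depend on any comparator. Entry to the analysis requires implantation, but the clock starts at an earlier scan. Nobody in the analysis could have died between the two. Patients who progressed and died before implantation, or became too ill for it, are absent. The curve from T0 therefore sits too high as an estimate of survival from T0. Set against patients counted from their own progression scan, it would favour the macrobeads even with no treatment effect.

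**Working it through.** **1. Is there a comparator anywhere in the SAP?** The numbered body, sections 1 to 16, is complete.

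| SAP section | What it provides for survival |
|---|---|
| 3.2 | "There are no pre-specified comparisons between the two cancer types" |
| 3.4 | 30 patients on practical grounds; no power, alpha or reference median |
| 5 | Implanted subjects only |
| 6.2 | All analyses exploratory, none confirmatory |
| 10, 10.1.1 | Kaplan-Meier with 95% intervals; no group comparisons planned |
| 10.2 | Medians; Cox models on the trial's own covariates; optional comparison by implantation number |
| 16.1 to 16.3 | No listing, table or figure with an external cohort |

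No external population, matching rule, benchmark or comparative survival test against one appears. The documents attach no figure to the promised comparison, so there is none to reproduce.

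**2. Which text governs?** The SAP overrides the protocol, so the governing plan is descriptive. The versions do not match. SAP 2 covers Amendment 10 (27 June 2013) and SAP 3.2 plans 30 subjects. The protocol is Amendment 11 (November 2014) with 74.

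**3. What if a comparison is done anyway?** This is an illustration on assumed inputs: exponential survival, all subjects dead, no true effect, and a two-sided 5% test against a fixed reference median. Let r be the trial patients' true median divided by the chosen reference, and d the number of deaths. The chance of a nominally significant benefit is Φ(√d × ln r − 1.96). Take d = 74 − 40 = 34 colorectal subjects (Protocol Appendix 3, item 9) or d = 20 (SAP 3.2).

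- r = 1.0: Φ(−1.96) = 2.5% for either d.
- r = 1.2: d = 34, Φ(5.831 × 0.1823 − 1.96) = Φ(−0.897) = 18.5%; d = 20, Φ(4.472 × 0.1823 − 1.96) = Φ(−1.145) = 12.6%.
- r = 1.5: d = 34, Φ(5.831 × 0.4055 − 1.96) = Φ(0.404) = 66%; d = 20, Φ(4.472 × 0.4055 − 1.96) = Φ(−0.147) = 44%.

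The SAP plans no such test. The figures show only how strongly an answer would depend on the reference chosen.

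**4. Guaranteed time from T0.** Let L be the T0-to-implant interval, taken as the same for everyone, and m the median from implantation. The implanted group's median from T0 is L + m. Neither L nor m is in the documents. Assume m = 6 months and L = 2 to 6 months. The median from T0 for all patients, had none been excluded for dying before implantation, depends on the hazard:

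- Constant hazard: it equals m, so the excess is L.
- Rising hazard (Weibull, shape 2): it equals √((L + m)² − L²).

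| L (months) | Implanted group, L + m | All patients, constant hazard (excess) | All patients, Weibull shape 2 (excess) |
|---|---|---|---|
| 2 | 8 | 6 (2) | √(64 − 4) = √60 = 7.7 (0.3) |
| 6 | 12 | 6 (6) | √(144 − 36) = √108 = 10.4 (1.6) |

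No document sets 2 months as a floor. Protocol 5.1.1 requires screening imaging within 21 days of the first implant, and T0 could be that scan. L could then be under a month and the excess smaller. A falling hazard would give an excess above L.

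**The case against.** Several points on the other side stand.

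- **The SAP sentence may be narrower than it looks.** It follows a statement about stratifying by cancer type, so it could mean only colorectal against pancreatic. SAP 3.2 already covers that pair, which favours the wider reading but does not prove it. A reader might infer that the two documents prescribe opposite analyses. On the narrow reading the SAP is merely silent on an external cohort. Either way it defines none.
- **The governing plan is already descriptive.** The SAP takes precedence and calls everything exploratory. Protocol Appendix 3 (item 9) says the primary objectives are met by estimation. A reader might infer that a comparator will be picked once results are known. No passage says so, and it is equally consistent with the text that no comparison will be made. SAP 10 lets further exploratory efficacy outcomes be defined in the study report, which leaves room for one but does not announce one.
- **A clean analysis exists.** Time from first implantation to death is a planned secondary analysis and contains no guaranteed time. It does not correct the primary one.
- **The curve from T0 describes implanted patients accurately.** That is true, but only conditionally on their having reached implantation. It is not survival from T0 for a group defined at T0.
- **A later SAP may exist.** Whether the copy attached to Amendment 11 is this one cannot be determined from the documents.

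**Conclusion.** The concern holds in two parts. First, Protocol 7.1 relies on an SAP definition that is absent from the SAP provided. Under that SAP the promised comparison is not planned; if carried out, it would have no prespecified comparator, and for colorectal cancer it would follow use of the data. Second, the primary survival estimate from T0 is biased upward, because T0 precedes implantation and only implanted subjects are analysed.

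The direction of that bias follows from the definitions. Its size does not. A reader might infer that an apparent median of 8 to 12 months could arise with no treatment effect. Those are simply L + m for an assumed 6-month median and an assumed interval of 2 to 6 months, and they are not the bias. On those inputs the overstatement is 2 to 6 months with constant hazard and 0.3 to 1.6 months with the rising hazard shown.

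The point weighs most on colorectal cancer, where the current protocol makes mortality primary. For pancreatic cancer its primary objective is response rate. Since all analyses are exploratory, this limits interpretation rather than invalidating a test. It should be corrected.

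**What to change.** (a) Reconcile Protocol 7.1 with the SAP in one of two ways.

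- Strike the sentence, and state that survival is descriptive and supports no efficacy comparison.
- Or specify the external cohort in the SAP: source, eligibility, the same T0 definition, and comparators alive and implant-eligible at the matched time from T0. Risk time must start at that matched point in both groups. If delayed entry were applied only to treated subjects while the selected comparators kept their earlier time, the guaranteed time would move to the comparators and bias the result against the macrobeads. Label any colorectal comparison post hoc.

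(b) In SAP 10.1.1, estimate survival from T0 with delayed entry (left truncation) at first implantation, and report it beside the planned time-from-implantation analysis. This assumes that the timing of implantation is unrelated to later prognosis. It removes the guaranteed time but not the selection of patients fit enough for implantation.

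(c) Align the time-origin labels. Table 14.2.4 and the mortality figure list in SAP 16.2 use the most recent progression scan, and SAP 10.2 plots time since implantation, whereas SAP 10.1.1 uses the first scan.

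Cost: striking the sentence costs nothing but limits the claim. Specifying a comparison needs SAP text and analysis work. Delayed entry needs a little programming, makes the early risk sets small and less stable, and will give a less favourable estimate from T0.
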